Protocol Title: Neuroplasticity Following Theta-Burst Stimulation in Cocaine Use Disorder

Abbreviated Title: TBS in Cocaine Use

Protocol Number: 17-DA-N002

Date of This Submission/Version: December 6, 2023

NCT02927236

NIH Principal Investigator:

[name]

Chief, Neuroimaging Research Branch

NIDA IRP

Biomedical Research Center

[name]

[name]

[contact] phone

[contact]

PRÉCIS:

Objectives: Illicit drug use affects tens of millions of Americans and costs nearly \$200 billion annually in health care costs and lost productivity. Cocaine dependence accounts for 25% of reported lifetime drug dependence though few successfully abstain with treatment. For efforts toward positive long-term outcomes, it is imperative to identify risk factors of poor outcomes, specialized treatments, neural mechanisms that change with treatment, and predictive measures of treatment outcomes. Substance abusers are known to have dysregulation in cue reactivity, reward processing, executive control, and intrinsic network connectivity. Non-invasive brain stimulation (NIBS) has proven effective at reducing drug craving in nicotine, alcohol, and cocaine users. Here, intermittent theta-burst stimulation (iTBS), a type of NIBS, delivered to left dorsolateral prefrontal cortex (dIPFC) is implemented to modulate substance abuse related circuit dysregulations and assess the relationship of iTBS-induced changes in circuitry to ongoing cocaine use.

Study population: Recruitment from the Baltimore, Maryland area will take place for this protocol. For the Pilot, 20 cocaine dependent (CD) individuals will be recruited. (The Pilot was completed in July 2018). For the Expanded Feasibility Study, 45 healthy adults (HC) and 90 CD individuals will be recruited. All of the HC group will receive **both active- and sham-iTBS in a within-subject crossover design. Half (45) of the CD group will receive active-iTBS and half (45) will receive sham-iTBS.** The Expanded Feasibility Study groups will be matched on demographic measures (e.g., age, IQ, sex).

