Presented here is a brief summary of cognitive and affective dysregulations previously identified in individuals with cocaine dependence, providing potential functional targets for therapeutic interventions. Ultimately, some of these targets may also serve as biomarkers for treatment efficacy. Overall, it is important to delineate the relationship between cocaine dependence and abnormalities in neural measures. Following this summary, a novel non-invasive brain stimulation (NIBS; intermittent theta-burst stimulation or iTBS) intervention is proposed. Several NIBS techniques have been implemented in an attempt to reduce craving for nicotine, alcohol, and cocaine, with repetitive transcranial magnetic stimulation (rTMS) as the most common NIBS applied. Implementation of iTBS can be less time consuming and found to be more tolerable by participants thus offering the potential for widespread application. This is an initial step toward developing a new, efficacious treatment for cocaine dependence.

A protocol is proposed with a Pilot designed to assess tolerability of iTBS parameters to employ in a subsequent Expanded Feasibility Study assessing neuroplasticity related to the intervention was completed. The iTBS experimental treatment will be an add-on to a contingency management (CM) treatment as usual (TAU) that has been implemented successfully to reduce cocaine use (albeit with minimal long-term efficacy following CM). Neural risk factors will be monitored during and after treatment to identify changes with treatment. Cocaine use will also be tracked to inform any neural changes and treatment efficacy. Malleable risk factors identified here will be prime targets for future studies and treatment development.

This proposal allows for a comprehensive neural picture of cocaine dependence. As discussed below, functional differences within tasks will be acquired with blood oxygenation level dependent (BOLD) fMRI and non-task related group differences will be identified with measures of structural, diffusion tensor imaging (DTI), functional connectivity (e.g., resting state measures), arterial spin labeling (ASL), magnetic resonance spectroscopy (MRS). Specific cognitive and affective constructs probed in this protocol are discussed in detail below. Changes in neural measures will be assessed in relation to reductions in cocaine use.

B. Dysregulation in Addiction

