1	4	1	5	5
1	4	2	10	15
1	4	3	10	25
2	5	4	20	45
2	5	5	20	65
2	5	6	20	85
3	6	7	20	105
3	6	8	20	125
3	6	9	20	145
4	7	10	30	175

4	7	11	30	205
4	7	12	30	235
5	8	13	40	275
5	8	14	40	315
5	8	15	40	355
6	9	16	40	395
6	9	17	40	435
6	9	18	40	475
7	10	19	40	515
7	10	20	40	555
8	11	21	40	595
8	11	22	60	655
9	12	23	60	715
9	12	24	60	775
10	13	25	60	835
10	13	26	80	915
11	14	27	80	995
11	14	28	80	1,075.00

Introduction to Treatment: Before initiation of iTBS, a session will take place to assess and attempt to enhance individual motivation and preparation to reduce or eliminate cocaine use. During this session, participants may repeat some assessments, such as the BCCMA. This session is designed to inform the participant of the treatment trajectory, introduce the concept of CM, introduce techniques to manage cue-induced craving, and assess and enhance their motivation to quit using cocaine. This will be conducted by the MAI, study therapist, or designee.

F. Inclusion and Exclusion

i. Description of the Study Population

We will enroll 45 (within-subject crossover active- vs sham-iTBS manipulation) HC and 90 treatment seeking CD (45 active-iTBS and 45 sham-iTBS) individuals who meet the inclusion and exclusion criteria. Fifty CD participants in each group will be recruited

to obtain the necessary number of (n = 30) treatment completers (see power analysis; calculated to ensure necessary power for MRI measures). Screening will be conducted under the approved NIDA IRP general screening protocol to determine eligibility (Expanded Feasibility Study Eligibility Checklist; Appendix 31). Participants will also be required to enroll in the NIDA protocol 10-DA-N457 to gather characterization data not otherwise collected in this protocol but which will be used in the planned analyses. Generally, CD participants will be current cocaine users and HC participants will be non-users matched on measures including age, sex, ethnicity, race, etc.

ii. Inclusion Criteria

1. Be able to give valid informed consent.
2. Agree to also participate in study 10DAN457, where characterization information is gathered and shared with this protocol.
3. Be 22 – 60 years of age.
 - a. Justification: Many neural processes change with age, and these changes could introduce unwanted variability in both behavioral and MRI signals.
 - b. Screening tool: Self-report.
4. Right-handed.
 - a. Justification: Differences in hemispheric dominance could confound iTBS administration and MRI measurements.

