 - a. Justification: MRI is the primary data gathering tool
 - b. Screening tools: current clinical procedures in use at the NIDA IRP

iii. Exclusion Criteria

1. History of any neurological disorder that would increase seizure risk from iTBS such as stroke, brain lesions, previous neurosurgery, any history of seizure or fainting episode of unknown cause, or head trauma resulting in loss of consciousness, lasting over 30 minutes or with sequela lasting longer than one month.
 - a. Justification: Stroke, vascular lesions or head trauma can lower the seizure threshold and are therefore contra-indications for iTBS. Fainting episodes or syncope of unknown cause could indicate an undiagnosed condition associated with seizures.
 - b. Screening tool: TMS safety Screen and Medical History.
2. Current DSM-5 moderate-severe substance use disorder on a substance other than cocaine, nicotine, marijuana, or opiates (provided they are currently stable on a medication assisted treatment) or meeting withdrawal criteria for a sedative/hypnotic/anxiolytic, or tolerance criteria in an individual using 3 or more days/week, regardless of diagnosis. Individuals will be considered stable on a maintenance medication if they have been on a stable dose for at least 2-weeks prior to consenting to 17-DA-N002 and have provided at least 3 urine specimens negative for illicit opioids over the same 2-week period (10 business days) with at least one test collected within two business days of the start of the period, one collected within three business days of the end of the period and one collected at least two days from either

of the other two specimens. Urine results may be gathered at NIDA as part of screening or be provided by the buprenorphine maintenance prescriber.

Communication between the maintenance provider and the MAI (or covering Staff Clinician) will be ongoing to establish continued illicit opioid abstinence between participant clearance and consent to 17-DA-N002.

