- a. Justification: While use of multiple substances is the norm and some use will be allowed, the focus of the current protocol is on cocaine. However, participants with tolerance or withdrawal symptoms to a sedative/hypnotic/ anxiolytic will be at increased risk of a seizure from iTBS and will therefore be excluded. Alcohol withdrawal will be assessed on ITBS days and rescheduled if in withdrawal. Individuals receiving maintenance treatment for OUD and struggling with cocaine use are an ecologically valid population in the greater Baltimore area and do not increase risk of seizure.
- b. Screening tool: Drug Use Survey and SCID-research version.

3. HC participants will not currently meet DSM-5 criteria for moderate to severe substance use disorder (excluding nicotine), and in the past, will not meet DSM-5 criteria for moderate to severe substance use disorder for cannabis or alcohol in the past 5 years or ever for other illicit substances. HC will not meet current withdrawal criteria for alcohol or sedative/hypnotics/anxiolytics, or tolerance criteria in an individual using 3 or more days/week. Urine toxicology positive for any illicit substance inconsistent with history given will also be exclusionary.

- a. Justification: The population of interest is a healthy control population with no substance use disorder. Current use of illicit substances or alcohol could impact on seizure threshold and is therefore contraindicated for iTBS.
- b. Screening tools: SCID-research version. Potential diagnoses will be further evaluated by a counsellor, Drug Use Survey (DUS), Substance

Use Disorder Evaluation, Medical Assessments: urine qualitative drug screen is performed for cocaine, THC, benzo, morphine/opiates, MDMA, amphetamine /methamphetamine, methadone, buprenorphine, PCP, and oxycodone.

4. First-degree family history of any form of epilepsy with a potentially hereditary basis .
 - a. Justification: First-degree family history of epilepsy with a hereditary component increases the risk of the participant having an undiagnosed condition that is associated with lowered seizure threshold.
 - b. Screening tool: TMS safety screening, Medical History.

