Protocol completers are defined as CD participants who complete 10 iTBS days of treatment within 3 weeks and visit 19 (first post-treatment scan day). CD participants who complete at least 5 iTBS treatment days in 3 weeks are eligible to begin with CM and follow-up visits. All study visits, including those with MRI scans, will be offered to these individuals as if they had completed all 10 iTBS treatment days. An HC participant is considered a protocol completer after completing all scheduled visits (baseline characterization visits and 2 iTBS treatment days with MRI scans).

Overall, CD participants will complete about 43 visits and HC participants 5 visits, with 8 and 6 MRI scans collected for CD and HC participants, respectively. Most of the visits for CD participants will be to collect urine samples and implement CM. The order of procedures completed during each visit may vary slightly, depending on availability of staff and other resources (mock scanner, MRI, study rooms, etc.).

Each study visit day will start with a brief nursing assessment that includes a urine sample for drugs of abuse, a breathalyzer, and vital signs. A urine pregnancy test for females will occur weekly during the iTBS treatment and any visit that includes an MRI scan thereafter. If breathalyzer is positive for alcohol participants may be rescheduled. In the event of a positive drug test, an interview to assess last drug use and a neuromotor assessment to test for acute intoxication will be performed. If participants test positive for drugs other than marijuana, based on MAI judgment, they may be rescheduled. If urine is positive for other illicit drugs, and if there are no known TMS contraindications, the participants may be allowed to participate at the discretion of the MAI. Otherwise, participants will be rescheduled. The CD group is expected to be current users and will likely test positive for illicit drugs. These procedures are designed to identify if CD participants are currently impaired and if HC participants have recently used illicit or licit drugs. Participants who smoke will be allowed breaks to smoke to preclude acute nicotine withdrawal. If a participant runs out of cigarettes, we will provide them on an as-needed basis to avoid withdrawal, which requires us to reschedule the visit. All study visits will take place at National Institute on Drug Abuse Intramural Research Program (NIDA-IRP).

1. Screening

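### The CD–HC contrast is attributed to cocaine, but eligibility lets cannabis and maintained opioid use disorder differ between the groups by design, and the analysis does not address it

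*Combined protocol and SAP*

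**What the plan says.** **Aim of the contrast.** Section I.A (The Problem) says that "it is important to delineate the relationship between cocaine dependence and abnormalities in neural measures". The baseline CD–HC difference is the first of the two main comparisons in the Précis (Outcome parameters), and it is Aim 1 and Hypothesis 1 in III.C and III.D. Hypothesis 5 also uses HC as the reference that treated CD are expected to approach.

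**CD eligibility (III.F.iii, item 2).** Current moderate-to-severe disorder is exclusionary on a substance "other than cocaine, nicotine, marijuana, or opiates (provided they are currently stable on a medication assisted treatment". The justification to that item adds: "While use of multiple substances is the norm and some use will be allowed, the focus of the current protocol is on cocaine".

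**HC eligibility (III.F.iii, item 3).** "HC participants will not currently meet DSM-5 criteria for moderate to severe substance use disorder (excluding nicotine". Past moderate-to-severe disorder is also barred, "for cannabis or alcohol in the past 5 years or ever for other illicit substances".

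**Matching.** The Précis says the "groups will be matched on demographic measures (e.g., age, IQ, sex". Section III.F.i says "HC participants will be non-users matched on measures including age, sex, ethnicity, race, etc". Neither list names smoking. Both are open-ended.

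**Smoking during visits (III.G.i).** "Participants who smoke will be allowed breaks to smoke to preclude acute nicotine withdrawal".

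**Analysis (III.G.vi).** CD and HC are to be compared with between-group tests, and an independent-samples t-test is the example given. The only covariate named in that section is the number of iTBS days, and it is conditional on poor completion. No restriction, stratum, covariate or sensitivity analysis is given for other substances.

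**The concern.** The contrast is meant to show what goes with cocaine dependence, yet the two groups can differ in other substance exposures that the protocol itself treats as relevant to the brain. Section I.B describes network connectivity differences in users of other substances as well as cocaine. Exclusion item 7 keeps out psychotropic medication partly because it could change neural function for reasons unrelated to the participant's drug use. Item 2 nevertheless admits opioid maintenance medication in CD. Its justification concerns seizure risk and how representative such patients are locally. It does not discuss what this does to the comparison with HC.

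If cannabis use disorder or opioid maintenance affects resting connectivity, perfusion or task activation, the plan as written would report that effect as cocaine-related dysregulation. The same shift would enter the HC benchmark in Hypothesis 5: part of the gap to be normalized would not be a cocaine gap.

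**Working it through.** **1. Which exposures differ, and why.**

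| Exposure | CD | HC | Difference between groups |
|---|---|---|---|
| Moderate-to-severe cannabis use disorder | allowed, current | barred, current and past 5 years | built in |
| Opioid use disorder on maintenance medication | allowed if stable | barred | built in |
| Nicotine use disorder | allowed | allowed | possible, not built in |

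For the first two rows, HC prevalence at that severity is zero by rule, so the gap equals whatever prevalence occurs in CD. HC may still have milder cannabis use. For nicotine, no criterion forces a gap and it could be zero.

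**2. Figures in the plan.** The protocol gives no sample-size calculation for CD versus HC, so there is no figure of its own to reproduce here. It does cite a published CD–HC functional connectivity effect of 0.67 (III.G.vi), used below only as a yardstick.

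**3. Size of the bias (illustration).** Let p_CD and p_HC be the prevalences of another exposure and δ its effect in SD units, acting additively. Then

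bias in the CD–HC difference = (p_CD − p_HC) × δ.

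The documents give neither prevalences nor effects. The assumed range is a gap of 20 to 60 points and δ of 0.2 to 0.5 SD. Each cell shows the bias in SD and its share of 0.67.

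| Gap | δ = 0.2 | δ = 0.3 | δ = 0.5 |
|---|---|---|---|
| 20 points | 0.04 (6%) | 0.06 (9%) | 0.10 (15%) |
| 40 points | 0.08 (12%) | 0.12 (18%) | 0.20 (30%) |
| 60 points | 0.12 (18%) | 0.18 (27%) | 0.30 (45%) |

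For example, 0.2 × 0.2 = 0.04 and 0.04 / 0.67 = 6%; 0.6 × 0.5 = 0.30 and 0.30 / 0.67 = 45%. The bias has the sign of δ, so it could hide a cocaine effect as well as imitate one.

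**4. Price of restricting the CD group.** In SD units, the standard error of a mean difference is √(1/n_CD + 1/n_HC). At the planned enrolment of 90 and 45 it is √(1/90 + 1/45) = 0.183. The share of CD that would be excluded is not given, so a range is assumed:

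- 20% excluded (72 left): √(1/72 + 1/45) = 0.190, intervals about 4% wider.
- 40% excluded (54 left): √(1/54 + 1/45) = 0.202, about 11% wider.
- 60% excluded (36 left): √(1/36 + 1/45) = 0.224, about 22% wider.

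**The case against.** Several points on the other side are sound.

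- **Broad enrolment is deliberate.** The protocol expects multiple substance use and defends maintained patients as representative of the local population. That is a reasonable choice and is not challenged here; what is missing is its handling in the CD–HC analysis.
- **Smoking.** A reader might infer that a smoking difference is built in, or that the groups are deliberately left unmatched on it. The documents do not support that. Nicotine use disorder is allowed in both groups, both matching lists are open-ended, and the smoking breaks apply to everyone to prevent withdrawal. What stands is that matching on smoking is not specified.
- **False-positive rate.** A reader might put these biases through a t-test at 0.05 and quote an inflated error rate for the imaging results. Section III.G.vi assigns 0.05 to behavioral and questionnaire data, while imaging is cluster-corrected and the power text treats p < 0.002 as closer to such a threshold. With assumed inputs as well, no error rate should be quoted for those tests.
- **The t-test is an example.** The section also mentions factorial models and reserves the right to change methods. That freedom is not a plan for this problem.
- **Data may exist elsewhere.** Characterization data from the companion protocol 10-DA-N457 will be used, and its content cannot be seen here. The descriptions of the Drug Use Survey and the timeline follow-back do not name tobacco, so its capture has to be confirmed.

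**Conclusion.** The concern holds for the CD–HC contrast: Aim 1, Hypothesis 1, and the HC reference in Hypothesis 5. Moderate-to-severe cannabis use disorder and maintained opioid use disorder can occur in CD and not in HC, and no planned analysis separates them from cocaine. Smoking adds a possible imbalance that the plan leaves open.

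The size is unknown. The 0.04–0.30 SD range rests wholly on assumed prevalence gaps and effects and on additivity. It shows that the bias could run from minor to nearly half of the effect cited.

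A reader might go further and infer that the active–sham result is compromised. It is not: that comparison is randomized within CD, so these exposures do not confound it. Nor does the point show that any CD–HC finding would be false, only that its attribution to cocaine would be unsupported as planned. This is an inexpensive improvement to a main comparison, and no eligibility rule needs to change.

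**What to change.** 1. **Restricted analysis.** Repeat each CD–HC contrast after leaving out CD on opioid maintenance and CD with current moderate-to-severe cannabis use disorder. Report full and restricted estimates with 95% intervals. Call a difference cocaine-related only if the restricted estimate keeps its direction and stays within a margin fixed before analysis, for example no more than 25% smaller. Otherwise describe it as a difference between CD with co-occurring substance use and HC. A covariate does not replace this step: with no exposed HC, its coefficient comes from CD alone and supplies no exposed comparison across groups. The diagnoses are already collected through the SCID and Drug Use Survey.

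2. **Smoking.** Name smoking status as a matching variable for HC still to be recruited, and add a smoking-adjusted CD–HC analysis from the recorded substance-use history, after confirming that it captures tobacco. Adjustment can work here because both groups may include smokers.

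**Cost.** One more matching variable, whose benefit depends on how many HC remain (not stated), and two further analyses on existing data if tobacco is captured. The restricted set is smaller, so its intervals are wider: about 4–22% if 20–60% of CD are left out. Milder cannabis use in either group is not removed by the restriction and should be reported as a limitation.
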